7.2.2 Inclusion Criteria

Patients eligible for inclusion in this registry have to meet **all** of the following criteria:

- 1. Male or female, pediatric patients aged greater than 1 year (≥365 days) and less than 18 years old (<17 years, 365 days) at diagnosis.
- 2. Documented, newly diagnosed Philadelphia Chromosome-positive (Ph+) acute lymphoblastic leukemia (ALL).
 - Recorded presence of t(9;22)(q34;q11) is required e.g. determined via institutional cytogenetics or FISH and/ or of the presence of BCR-ABL fusion transcript identified by RT-PCR or FISH.
- 3. Enrolled into this registry within 6 months of diagnosis or enrolled in a clinical trial within 6 months of diagnosis, although no earlier than Jan-2012.
- 4. Previously treated or currently on treatment with any chemotherapy regimen + imatinib (of an HA-approved formulation or HA-approved Glivec[®] generic) ± HSCT.
- 5. Written informed consent obtained prior to any information being entered into the registry (parent / legal guardian consent, where applicable).
 - Assent from a patient enrolled as a minor by parent / legal guardian consent **must** be obtained wherever possible. Obvious child dissent **must** be respected.
 - A patient enrolled as a minor by parent / legal guardian consent **must** be re-consented as an adult upon reaching the legal age of maturity during the course of the registry (legal age of maturity defined by local regulations).
 - Patients fulfilling the inclusion criteria, but who have died prior to registry opening and without the opportunity to give consent, may still be eligible for inclusion, subject to local requirements regarding the consent process.

The registry participating physician must assess whether there are any third-party agreements limiting the clinical trial patient's data collection as part of the non-interventional study given that no identification of proprietary treatment information will take place.

7.2.3 Exclusion Criteria

There are **no** exclusion criteria for this non-interventional study.

Patients may voluntarily withdraw from the registry at any time.

7.2.4 Reasons for non-inclusion

The reasons for non-inclusion in the registry will be recorded during pre-screening and classified as:

- Did not meet diagnostic criteria
 - Patients for whom the presence of t(9;22)(q34;q11) could not be determined/ confirmed or for whom diagnosis occurred outside of the specified age range or for whom diagnosis was greater than 6 months before first treatment.
- Subject consent not given (e.g. either by parent/ legal guardian or subject themselves)

- Alternative treatment choice (e.g. physician's decision not to treat with imatinib or to treat with a non-HA-approved, Glivec[®] generic).
- Unknown
- Other (please specify)

7.2.5 Reasons for discontinuation

The reasons for discontinuation from participation in the registry will be collected and classified as:

- Death
 - For patients who discontinue due to death, then 'Death' will be recorded as reason for discontinuation. Patient's date of death, cause of death and phase of disease during which death occurred will be recorded, as permitted by local regulations.
- Lost to follow up
 - Patients lost to follow up should be recorded as such on the CRF. For patients who are lost to follow-up, the treating physician and/ or designee should show "due diligence" by documenting in the source documents steps taken to contact the patient, e.g. dates of telephone calls, registered letters, etc.
- Subject withdrew consent
- Administrative problems
- Treatment duration completed / condition no longer requires treatment
- Protocol deviation

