Population	The study population will include male or female pediatric patients (ages 1 to <18 years old) with documented, newly diagnosed Ph+ ALL who enrolled into this registry within 6 months of diagnosis or were enrolled in a clinical trial within 6 months of diagnosis (although no earlier than Jan-2012), and who were previously treated or are currently on treatment with chemotherapy + imatinib ± HSCT. Long term safety and efficacy data will be collected such that the observational follow-up data for each patient will be a minimum of 5 years from start of imatinib treatment. The registry has a planned enrollment of a minimum of 50 patients.
Variables	EFS, defined as time from diagnosis to relapse at any site, development of a second malignant neoplasm or death. OS, defined as time from diagnosis to death from any cause. Safety defined as adverse events and serious adverse events in the observation period.
Data sources	The data for this study will be retrieved from hospital discharge files, clinical records and electronic medical records.
Study size	50 patients
Data analysis	All data analyses will be performed by Novartis personnel and/ or designee. All data summaries and analyses will have descriptive purposes only. Patient efficacy, safety and tolerability outcomes of patients treated with chemotherapy + imatinib will be summarized overall, by HSCT (yes/ no) and risk group (good risk– induction responder/ poor risk– induction non-responder).
Milestones	Start of data collection: 14 July 2014 Study progress report(s): Yearly update (Q4) Planned final report of study results: June 2022

3 Amendments and updates

Amendment 2

The main purpose of this amendment is to change in the reference safety information for Glivec (imatinib).

Novartis has taken the decision to discontinue the use of the Investigator's Brochure for Glivec \mathbb{R} (imatinib), since Glivec has been on the market for more than 15 years (first registered in 2001) and has a well-established efficacy/safety profile. In addition, there is no further global clinical development planned for the compound.

As of the dispatch of the Glivec DSUR 006 in July 2017, the latest approved national/regional product label (e.g. in the EU Summary of Product Characteristics) will serve as the reference safety information (RSI) for the compound.

The Glivec Investigator's Brochure version 19 (dated 21-Jun-2016) is the final Investigator's Brochure for the compound.

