At the time of this amendment, 44 patients were screened, 3 failed screening and 41 were enrolled. Enrollment was ongoing at the time of this amendment.

Amendment 1

The rationale for making the proposed changes in this amendment is based on the following points.

Accrual to this registry has been challenging for many reasons. First, Ph+ ALL in the pediatric population is a rare condition. As such, finding patients for the registry has been

Novartis	Confidential	Page 9
Non-interventional study protocol - v02 (Clea	in)	STI571 / Glivec® / CSTI571I2201

more difficult than previously projected. In addition, imatinib is not yet available for all countries for the pediatric indication. Given these reasons, and in light of the need to provide adequate 5-year follow up on the study population in a timely manner, it has been decided to amend the number of patients to be studied from 100 to a minimum of 50. Other changes have been included now as well reflecting administrative updates. These are delineated in the table below.

At the time of this amendment, 17 patients were screened, 3 failed screening and 14 were enrolled. Enrollment was ongoing at the time of this amendment.

Number	Date	Section of study protocol	Amendment or update	Reason
1	01-Feb-2016	Section 4	Study milestone dates revised	Updated to reflect current status
1	01-Feb-2016	Section 6	Acute or chronic added to incidence of graft versus host disease	To be consistent with Section 7.7.4.3
1	01-Feb-2016	Section 7.1.1	Patient population reduced to a minimum of 50	Recruitment efforts during the first year confirmed the rarity of this patient population. The sample size has been changed to 50 pts accordingly.
1	11-May- 2016	Section 7.1.4	Definition of end of study further clarified	Clarify each patient will have a minimum of 5 years of follow up from the start of imatinib treatment
1	01-Feb-2016	Section 7.2.5	Disease progression removed from the list of potential reasons for study discontinuation	Not applicable to this study
1	01-Feb-2016	Section 7.3.1.6	Added/clarified definitions of time to engraftment and engraftment failure	For clarity
1	01-Feb-2016	Section 7.3.1.8	Revised definition of AE reporting period	For consistency
1	01-Feb-2016	Section 7.3.1.9	Duration of treatment for assessment of drug exposure further defined	For clarity

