7.1.4 Definition of the end of study

The end of study is defined as the point when a minimum of 5 years of observational followup data are available for each enrolled patient, or such available data until early discontinuation (Section 7.2.5), as measured from the date of start of imatinib treatment.

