7.4.1 Data collection schedule

This is a non-interventional registry and does not impose a therapy protocol, diagnostic/ therapeutic procedure, or a visit schedule. Patients will be treated according to the local prescribing information, and routine medical practice in terms of visit frequency and the types of assessments performed for disease evaluation, and only these data will be collected as part of the registry. The treating physician and/ or designee are asked to complete the appropriate electronic Case Report Form (eCRF) at every patient visit, where possible. For each patient enrolled in the registry a minimum of a once yearly update (12 ± 2 month intervals) of data in the registry database must occur to ensure an ongoing data stream, with the exception of safety data which should be entered within a month of new information becoming available. Where disease evaluation is performed frequently, any follow-up information collected that is relevant to the objectives of this registry should be recorded in the database. Long term safety and efficacy data will be collected such that the observational follow-up for each patient will be a minimum of 5 years from start of imatinib treatment or such available data until early patient discontinuation (Section 7.2.5).

Table 7-1 is a data collection schedule that outlines all the assessment information required by the registry and indicates with an "X", the visits when they are recorded. All data obtained from these assessments must be supported in the patient's source documentation. The table indicates which assessments produce data to be entered into the clinical database (D) or remain in source documents only (S) ("Category" column). The expectation is that laboratory assessments/ interventions shown are those required for the standard disease management of pediatric Ph+ ALL, according to local best practice.

• Where complete laboratory assessments/ interventions are not performed, it will be acceptable to indicate not done.

For each patient discontinuation, the reason for discontinuation should be determined.

Novartis Non-interventional study protocol – v02 (Clean)

Confidential

Table 7-1Data collection schedule

			Surve		Surveillance	urveillance Period			
	tegory	Protocol	reening rollment	agnosis Iseline	On Treatment Follow-Up	End of study Treatment (EOT)	Post- Treatment Follow-Up	Study Evaluation Completion	Survival follow-up
	ပီ	Section	ыs	Ba	Visit Dates	EOT Date	Visit Dates	EOS Date	SURV Visit

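### Finishing treatment is listed as a reason to leave the registry, which lets a patient exit before year 5, still count as complete, and weaken the 5-year EFS estimate

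*Protocol*

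**What the plan says.** Section 7.2.5 of the Protocol opens with "The reasons for discontinuation from participation in the registry will be collected and classified as", so the list concerns leaving the registry, not stopping imatinib. Beside death, loss to follow-up, withdrawn consent, administrative problems and protocol deviation, it contains "Treatment duration completed / condition no longer requires treatment".

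The list has consequences elsewhere. Section 7.1.4 places the end of study at the point when "a minimum of 5 years of observational followup data are available for each enrolled patient", counted from imatinib start, and then accepts whatever data exist up to early discontinuation, citing Section 7.2.5. Section 7.4.1 carries the same exception with the same cross-reference. The Population entry of the Abstract omits the exception: "the observational follow-up data for each patient will be a minimum of 5 years from start of imatinib treatment".

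Table 7-1 keeps four steps apart: end of treatment (visit 777), "Post- Treatment Follow-Up" (602), study completion (778) and survival follow-up (888). Section 7.7.4.1 censors EFS at last contact for patients without an event.

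On timing, the Abstract gives "Planned final report of study results: June 2022". Section 7.1.3 places the final analysis after the end of study. Section 3 records that at Amendment 2 "44 patients were screened, 3 failed screening and 41 were enrolled", with enrolment still open. Section 7.5 asks for at least 50 patients.

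**The concern.** Exceptions to a 5-year minimum for death, loss to follow-up or withdrawn consent cannot be avoided. An exception for planned completion of treatment is a choice, and it works against the purpose of the study. A site that selects this exit reason breaks no rule, and the patient then satisfies the end-of-study definition with less than 5 years of data.

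The primary objective is long-term EFS, with relapse, second malignancy and death as events. Follow-up after imatinib ends is part of what a 5-year registry adds. No analysis plan can restore follow-up that was never collected, so the point has to be settled in the protocol and the eCRF.

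A related question is whether the planned report date leaves room for every patient to reach 5 years.

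**Working it through.** **1. The passages side by side**

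| Place | What it implies for a patient who finishes imatinib before year 5 |
|---|---|
| Section 7.2.5 | May be recorded as having left the registry |
| Sections 7.1.4, 7.4.1 | Data up to that exit are accepted in place of 5 years |
| Abstract, Population | 5 years are still required |
| Table 7-1 | Visits 602, 778 and 888 are still to come |
| Section 7.7.4.1 | If the patient has left, EFS is censored at last contact |

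The first two rows cannot be reconciled with the third and fourth.

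**2. Cost in precision**

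The protocol gives no precision figure to reproduce. Inputs from it are n = 50 (Section 7.5) and 69.6% EFS at 48 months in the continuous-imatinib cohort of the pivotal study (Section 5.3.1). Assumptions: a constant hazard; exits spread evenly over years 2 to 3, because the documents give no imatinib duration; exit unrelated to later risk; no other censoring before year 5.

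- Hazard: λ = −ln(0.696)/4 = 0.0906 per year.
- 5-year EFS: S = 0.696^(5/4) = 0.636.
- At risk at year 5 with no exits: 50 × 0.636 = 31.8.
- SD with no exits: √(0.636 × 0.364 / 50) = 0.068, or 6.8 points.

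If a share p leaves, the large-sample variance of the Kaplan-Meier estimate is (S²/n) × ∫₀⁵ λe^(λt)/G(t) dt. G(t) is the share not yet exited: 1 up to year 2, falling linearly to 1 − p at year 3.

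- Half leave: the integral over years 0–2, 2–3 and 3–5 is 0.199 + 0.158 + 0.521 = 0.878. SD = √(0.404 × 0.878 / 50) = 0.084.
- 80% leave: 0.199 + 0.231 + 1.304 = 1.734. SD = √(0.404 × 1.734 / 50) = 0.118.

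Simulated cohorts of 50 under the same assumptions give slightly larger values, because few patients remain at risk late on:

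| Share leaving | At risk at year 5 | Simulated SD (points) | 1.96 × SD (points) |
|---|---|---|---|
| None | 32 | 6.8 | 13.3 |
| Half | 16 | 8.5 | 16.7 |
| 80% | 6 | about 12.4 (12.3 to 12.8 between runs) | about 24.3 |
| All | 0 | not estimable | – |

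Mean estimated EFS stays near 0.636 with half or 80% leaving. If all leave, a curve carried flat from year 3 would read about 76% against a true 64%.

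**3. Margin in the report date**

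Patients still to enrol at Amendment 2: 50 − 41 = 9 at least. Amendment 2 entries run from 13 Feb to 27 Mar 2017 and Amendment 1 entries (14 enrolled) from 1 Feb to 11 May 2016. Accrual rates tried:

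- Stated in Section 7.1.1: 20/12 = 1.67 per month. The section adds that it may be less.
- Overall since 14 July 2014: 41 over 32.4 to 31.0 months = 1.26 to 1.32 per month.
- Between amendments: 41 − 14 = 27 over 13.8 to 9.1 months = 1.96 to 2.96 per month.

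The 50th enrolment is the amendment date + 9/rate. The last 5-year date is that date − lag from imatinib start to enrolment + 5 years. For direct entry the lag is 0 to 6 months, because entry must fall within 6 months of diagnosis (Section 7.2.2).

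| Rate | 50th enrolment | Last 5-year date, no lag | Last 5-year date, 6-month lag |
|---|---|---|---|
| 20 per year | 27 Jul–7 Sep 2017 | 27 Jul–7 Sep 2022 | 25 Jan–8 Mar 2022 |
| Overall observed | 8 Sep–29 Oct 2017 | 8 Sep–29 Oct 2022 | 9 Mar–29 Apr 2022 |
| Between amendments | 16 May–14 Aug 2017 | 16 May–14 Aug 2022 | 14 Nov 2021–12 Feb 2022 |

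Counting back from 30 June 2022, the last imatinib start must fall by 30 June 2017 with no reporting time, by 31 March 2017 with 3 months, and by 30 December 2016 with 6 months. The reporting times are assumptions.

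**The case against.** Section 7.2.5 classifies exits; it does not tell sites to close patients at the end of treatment. Section 7.1.1 counts any data from imatinib start onwards as follow-up, and Table 7-1 continues past visit 777. Most statements of the 5-year minimum are conditional by their own wording. The survival visit (888) would still capture deaths. The study is descriptive, with no hypothesis test. All of this stands. It makes the defect a contradiction to reconcile, not proof that follow-up stops with treatment. It does not remove the defect, because the condition on the 5-year minimum is the very list that contains treatment completion, and Table 7-1 schedules only overall survival at visit 888, not relapse or second malignancy.

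A reader might infer that patients doing well are the ones closed out, so that 5-year EFS is biased. The documents do not show that exit would be related to later risk, and exits unrelated to it cost precision while leaving the mean estimate unchanged, short of nearly everyone leaving.

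A reader might also infer that June 2022 falls before the last patients reach 5 years. The table above puts it before in some scenarios and after in others. Patients entering through a clinical trial may have started imatinib much earlier still, since trial enrolment counts from January 2012.

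Finally, nothing shows harm from keeping protocol deviation on the list; a deviation may properly end participation.

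**Conclusion.** The contradiction is firm and rests on text alone: Section 7.2.5, through Sections 7.1.4 and 7.4.1, permits what Table 7-1 and the primary objective rule out. Its size depends on how many patients would leave and when, which the documents do not say. Under the stated assumptions, the SD of 5-year EFS goes from about 6.8 points to 8.5 if half leave and about 12.4 if 80% leave; if all leave, the quantity cannot be estimated. The last case is an extreme that Table 7-1 argues against. Loss of precision is the main demonstrable cost; bias would need exit to be related to later risk.

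The report date is a secondary point. It has little or no margin: no imatinib start after June 2017 can have 5 years by June 2022, at least 9 patients were outstanding, and no enrolment closing date is given. The documents do not prove that the date is missed.

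**What to change.** Remove treatment completion from the exit reasons in Section 7.2.5 and record it only at the end-of-treatment visit (777). Add a sentence to Sections 7.1.4 and 7.4.1 that the end of imatinib does not end registry follow-up before 5 years from imatinib start. Leave protocol deviation on the list. This is about data collection only and implies nothing about how long imatinib is given.

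Give an enrolment closing date, and state the final-report milestone as last imatinib start + 5 years + reporting time.

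Cost: a short amendment, one change to an eCRF drop-down list, and possibly a later milestone to agree with the agency. No visits are needed beyond those in Table 7-1. The change secures follow-up for EFS. It does not by itself extend adverse event collection, for which Section 9.1 sets a minimum of 30 days (or 5 half-lives, if longer) after the last dose.

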7.3 Variables

A tabular overview of the main variables and their relationship to the defined objectives are outlined in Table 6-1.

The corresponding data collection schedule at each patient visit is contained within Table 7-1.

Detailed assessment information and the data to be collected, if available, are outlined in Section 7.4.2.

7.3.1 Outcomes of interest

7.3.1.1 Event free survival

- Event free survival is defined as time from diagnosis to relapse at any site, development of a second malignant neoplasm or death (Section 7.4.2.3)
 - Relapse at any site defined as BM (e.g. via bone marrow assessment) or CNS (e.g. via cerebro-spinal fluid exam) or testis or other sites or any combination.
 - Second malignant neoplasm defined as presence of any secondary malignancy.

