6 Research question and objectives

The main objective is to collect data to describe long-term clinical outcomes measured by event-free survival (EFS), overall survival (OS) and long-term safety in newly diagnosed Ph+ ALL pediatric patients treated with imatinib in combination with chemotherapy

This multi-center, registry is not designed to test a formal hypothesis, but has been initiated as part of the post-marketing commitment to the type II variation EMEA/H/C/000406/II/80, in order to address the limitations related to the limited size of the efficacy and safety database (up to 92 patients evaluated for efficacy and 220 patients evaluated for safety in prospective studies).

Objectives and related main variables under study are described in Table 6-1 below.

Confidential

Table 6-1 Objectives and related main variables

Objective	Main Variables	Analysis
Primary		Refer to Section 7.7
To evaluate long term clinical outcome measured by event-free survival (EFS, events defined as: relapse, death , secondary malignancies)	EFS, defined as time from diagnosis to relapse at any site, development of a second malignant neoplasm or death.	
Main secondary		
To evaluate overall survival	OS, defined as time from diagnosis to death from any cause.	
To evaluate safety	Adverse events and serious adverse events in the observation period.	
Other secondary		
To evaluate hematological remission status	Hematological remission status. Complete hematological remission requires that all of the following are present: a) Adequate bone marrow cellularity with a blast count < 5%, b) No peripheral blood blasts, c) ANC ≥1500/µl, d) Platelet count ≥100.000/µl, e) No evidence of extramedullary involvement	
To evaluate minimal residual disease (MRD) response	MRD response evaluated via detection of BCR-ABL transcript (e.g. determined via quantitative real-time PCR of mononuclear bone marrow and peripheral blood cells or detection by flow cytometry).	
To evaluate duration of complete remission	Complete remission and duration of complete remission (CR, defined as <5% blasts in bone marrow aspirate regardless of proportion of mature lymphocytes).	
To evaluate time to transplantation, time to engraftment, engraftment failure, graft versus host disease	Transplant and time to transplant from diagnosis. Time to engraftment and engraftment failure Incidence of graft versus host disease (acute and chronic)	

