7.4.2.2 Induction response

The patient response to induction treatment provides a measure of the patient-risk category. The commonly used definitions of good-risk (induction-responder) / poor-risk (induction non-responder) suggested below are adopted from Biondi et al. 2012. If this is not the definition that was used for a patient, information will be obtained with respect to the definition of risk.

- Good-Risk Group: Patients with both early response and complete remission at the end of induction e.g. Blast cell count < 1000/µl in peripheral blood after 7 days of Prednisone given in combination with chemotherapy drug(s) before induction is instituted or have M1/M2 BM at day 15 (after start of chemotherapy) or M1 BM at day 21 and achieve CR after induction period.
- Poor-Risk Group: Patients with poor early response to induction treatment or absence of complete remission at the end of induction e.g. Blast cell count ≥ 1000/µl in peripheral blood after 7 days of Prednisone given in combination with chemotherapy drug(s) before induction is instituted or have M3 BM at day 15 or M2/M3 BM at day 21 or do not achieve CR after induction period.
 - M1: <5% blasts, counting all nucleated cells, including erythropoiesis. In case of regenerating marrow with a high erythropoietic predominance, at least a total count of 100 non-erythropoietic cells should be counted.
 - M2: 5-25% blasts, counting all nucleated cells, including erythropoiesis. In case of regenerating marrow with a high erythropoietic predominance, at least a total count of 100 non-erythropoietic cells should be counted.
 - M3: >25% blasts in a BM aspirate.

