7.4.2.4 Hematological response

Peripheral blood will be used to assess hematological response. Complete hematological remission requires that **all** of the following are present:

- Adequate bone marrow cellularity with a blast count < 5%
- No peripheral blood blasts
- ANC $\geq 1500/\mu l$
- Platelet count $\geq 100.000/\mu l$
- No evidence of extramedullary involvement

The loss of complete remission and thus the end of the duration of complete remission is defined as:

• \geq 5% blasts in bone marrow aspirate regardless of proportion of mature lymphocytes.

Progressive disease (relapse) is defined as the new appearance of any of the following:

- $\geq 25\%$ blasts in bone marrow aspirate
- Any increase of at least 25% in the absolute number of circulating leukemic cells.
- \geq 30% increase of Ph+ metaphase cells as assessed by standard cytogenetic analysis.
- Development (evidence) of extramedullary disease
- Other laboratory or clinical evidence of disease progression.

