7.7.4.1 Primary endpoint

The **primary endpoint** will be event-free survival (EFS) considering the following events: relapse at any site, development of a second malignant neoplasm or death.

Event free survival is defined as the time from diagnosis to the earliest of these events.

Censoring date will be the date of last contact for patients who did not experience any of these events.

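### The primary EFS gives failure to reach complete remission neither an event nor an event date, so persistent leukemia without new progression counts as event-free time, mainly in the poor-risk group

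*Protocol*

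**What the plan says.** The Abstract, Table 6-1, Section 7.3.1.1 and Section 7.7.4.1 agree on the primary endpoint. Section 7.3.1.1 has "Event free survival is defined as time from diagnosis to relapse at any site, development of a second malignant neoplasm or death", Table 6-1 has "EFS, events defined as: relapse, death , secondary malignancies", and Section 7.7.4.1 has "event-free survival (EFS) considering the following events: relapse at any site, development of a second malignant neoplasm or death". Time runs from diagnosis. The censoring rule is also fixed: "Censoring date will be the date of last contact for patients who did not experience any of these events".

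Section 7.4.2.2 defines the risk groups by induction response. Good risk is "Patients with both early response and complete remission at the end of induction"; poor risk is "Patients with poor early response to induction treatment or absence of complete remission at the end of induction". It also allows another definition of risk where a patient was classified differently. Section 7.7 reports outcomes overall, by HSCT and by these risk groups.

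Section 7.3.1.1 describes relapse only by site and refers to Section 7.4.2.3. That section leaves relapse to the treating physician's tests and lists no criteria. The only relapse criteria are in Section 7.4.2.4, under hematological response: "Progressive disease (relapse) is defined as the new appearance of any of the following". The signs listed there include at least 25% marrow blasts, a rise of at least 25% in circulating leukemic cells, extramedullary disease, and other evidence of progression.

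**The concern.** An endpoint that starts at diagnosis needs a rule for patients whose leukemia never clears. Without one, a patient with stable persistent disease contributes event-free time until progression, second malignancy, death or last contact. That is the opposite of what an EFS curve is read to show.

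Under the default definition, good risk requires CR, so only the poor-risk curve can be raised. This can narrow the contrast between the two risk groups. It can also weaken the apparent effect of early response in the Cox models that Section 7.7.4.4 contemplates.

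There is a second gap. Because Section 7.3.1.1 does not say that the criteria in Section 7.4.2.4 apply, two sites could classify the same refractory patient differently for the primary endpoint.

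**Working it through.** The protocol has no figure to reproduce: Section 7.5 gives a minimum of 50 patients and no formal calculation.

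**Step 1: how a patient not in CR at the end of induction is handled as written.**
- *Marrow blasts never fall below 25%, nothing else changes.* The sign is not new, so Section 7.4.2.4 is not met. The patient has no event and is censored at last contact, or has an event at death.
- *Marrow blasts stay between 5% and 25%.* The patient is not in CR (Section 7.3.1.5 requires less than 5%) but is below the 25% marrow criterion. Again there is no event unless other progression is found.
- *Disease newly progresses.* If Section 7.4.2.4 governs EFS, this is a relapse dated at progression, which is later than the end of induction. If it does not govern, the handling is undefined.
- *CR is reached later (late remitter).* The patient can relapse and is counted in the usual way. This is not persistent leukemia.

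**Step 2: size.** Ignoring other censoring, at a time t after the end of induction:

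overstatement of EFS(t) = (k / n) × u

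where k is the number of never-remitting patients, n the group size, and u the share of the k with no counted event by t. The comparator is an EFS that counts these patients as events at the end of induction.

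From the protocol: N = 50. Assumed, because the protocol gives none of them: k = 1 to 5; poor-risk share 30% to 50%, so n = 50 × 0.3 = 15 to 50 × 0.5 = 25; u = 0.1 to 1.0; all k patients in the poor-risk group.

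Example with k = 2 and u = 0.5: overall 2/50 × 0.5 = 2.0 points; poor-risk 2/15 × 0.5 = 6.7 points or 2/25 × 0.5 = 4.0 points.

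| k | Overall, u = 0.1 / 0.5 / 1.0 | Poor-risk n = 15 | Poor-risk n = 25 |
|---|---|---|---|
| 0 | 0 / 0 / 0 | 0 / 0 / 0 | 0 / 0 / 0 |
| 1 | 0.2 / 1.0 / 2.0 | 0.7 / 3.3 / 6.7 | 0.4 / 2.0 / 4.0 |
| 2 | 0.4 / 2.0 / 4.0 | 1.3 / 6.7 / 13.3 | 0.8 / 4.0 / 8.0 |
| 3 | 0.6 / 3.0 / 6.0 | 2.0 / 10.0 / 20.0 | 1.2 / 6.0 / 12.0 |
| 5 | 1.0 / 5.0 / 10.0 | 3.3 / 16.7 / 33.3 | 2.0 / 10.0 / 20.0 |

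Entries are percentage points. Good risk is 0 under the default definition.

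**Step 3: reading the table.** u is close to 1 soon after induction and falls as patients progress or die. The right-hand value in each cell therefore belongs to the early curve. At 5 years a high u would mean years of persistent leukemia without progression or death, which is hard to square with the poor prognosis described in Section 5.2. For true never-remitters, the main long-term effect is a delayed event date.

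**The case against.** A reader might infer that refractory patients cannot relapse and are event-free until death. The documents do not support that. Section 7.4.2.4 equates progressive disease with relapse, requires no prior CR, and has a catch-all for other evidence of progression. A growing refractory leukemia can therefore be an event before death, a second malignancy also counts, and a living patient without an event is censored at last contact. What survives is persistent disease without new progression, the delayed date, and the open question of whether Section 7.4.2.4 governs EFS at all.

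A reader might also take the larger poor-risk figures as the expected bias. They rest on assumptions alone. Counting late remitters among the failures would inflate them further, and that part would measure a change of definition rather than an error.

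Nor do the documents support saying that the registry EFS is not comparable with the 48-month rates of 69.6% and 31.6% in Section 5.3.1. The protocol does not say how non-remission was counted there, it plans no formal comparison, and Section 7.9 acknowledges the lack of an external control.

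Two further arguments carry less weight. CR and CHR rates are reported separately with confidence intervals, so non-remission will be visible, but that does not correct the EFS curve. A sensitivity definition could be left to the analysis plan, and Section 7.7.4.4 already foresees other endpoint definitions. However, the protocol itself fixes the events and the censoring, and its only worked example of another definition concerns transplant.

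**Conclusion.** The point holds in this form: the primary EFS has no event or event date for failure to achieve CR, and it is unclear whether the relapse criteria in Section 7.4.2.4 apply to patients never in CR. EFS can be overstated and events delayed, mainly early in the curve and in the poor-risk group. Concentration in that group is expected but not guaranteed, because other risk definitions are allowed.

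The protocol gives no induction-failure rate and no poor-risk share, so the size cannot be derived from it. Under the assumptions above, 1 to 5 never-remitters in 50 would raise EFS by 0.2 to 10 points overall and 0.4 to 33.3 points in the poor-risk group, with the upper ends applying early. If every patient reaches CR, the effect is zero. In a descriptive registry this is a cheap improvement, not a flaw that invalidates the endpoint.

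**What to change.** Keep the primary definition, and make two changes:

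1. In Sections 7.3.1.1 and 7.7.4.1, state whether the relapse criteria of Section 7.4.2.4 govern EFS and whether they apply to patients never in CR. Correct the cross-reference to Section 7.4.2.3 accordingly.
2. In Section 7.7.4.4, add a sensitivity EFS, overall and by risk group, in which failure to reach CR by the end of the patient's own induction is an event at that date. Report the number affected, with never-remitters separated from late remitters.

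The cost is a few sentences and one repeated Kaplan-Meier analysis. Marrow assessments and induction response are already in Table 7-1. Some derivation work is needed, because any chemotherapy regimen is allowed, induction end dates and risk definitions vary, and data are collected only if available. The Poor/Good field alone will not do, since a poor early responder who reaches CR is also poor risk. The sensitivity estimate will be somewhat less favourable.
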